D.5.3. Follow-up Assessment: Following completion of treatment, participants will attend Post-Treatment Assessment monthly for 2 months (total of 02 follow-up visits). Each visit will take about 2 hours. Follow-up assessments will involve self-report for PTSD symptoms (PCL-5), cognitive assessment (CogState), depressive symptom severity (MADRS), clinical impression of illness severity and improvement (CGI), as well as self-reported measures of pain intensity (NRS for pain), level of anxiety (BAI), suicide risk (C-SSRS), general adverse events (PRISE/FIBSER) and quality of life (WHOQOL-BREF). The CAPS-5 will be administered once at 2-month follow-up.

Table 5: General Assessment Schedule

Construct	Measure	Eligibility and Baseline Assessment	Treatment Assessments	Follow-Up Assessment
		1-2 weeks	Week 1 to 12	2 months
Primary Outcome Measure				
PTSD symptoms	CAPS-5	X	X	X
Interview Based Assessments				
Decision-making capacity	Dysken Screening Tool	X		
PTSD severity	PCL-5	X	X	X
Diagnostic interview for comorbid conditions	M.I.N.I.	X		
Rule-out moderate/severe cognitive impairment	MMSE	X		
Infusion Safety Measures				
Physical Exam/ECG/Pregnancy test/Urine toxicology		X		
Recovery from infusion	mAldrete		X	
Side Effects (dissociative, psychotogenic, and manic symptoms)	CADSS, BPRS+, YMRS		X	
Secondary Outcome Measures				
Subjective units of distress (a proxy for extinction)	SUDS		X	
Cognitive function	CogState	X	X	X
Depressive Symptoms	MADRS	X	X	X
Suicide Risk	C-SSRS	X	X	X
Anxiety Symptoms	BAI	X	X	X
Pain Intensity	NRS	X	X	X
Quality of Life	WHOQOL-BREF	X	X	X
General Adverse Events	PRISE/FIBSER		X	X
Global Rating of Illness Severity and Improvement	CGI	X	X	X
Credibility/Expectation of Outcome Treatment	CEQ	X		

D.5.4. Independent Evaluation Integrity: The PI will oversee assessment core to ensure that independent evaluators will 1) undergo standardized training in all assessment instruments, 2) demonstrate reliability of

assessment at the beginning of the protocol; and 3) receive reliability checks on their evaluations throughout the protocol. Initial competency will be established by on-site didactic training for all clinical assessments and data collection procedures followed by the establishment of inter-rater reliability. Inter-rater reliability will be accomplished using a train-to-criterion protocol with recorded patient interviews (for symptom scales all total scores will be required to be within 2 points of the standardized score and all individual item scores were required to be within 1 point of the standardized score; for diagnostic assessments 100% agreement will be required for the primary diagnosis). To maintain competency and reduce “drift,” in-person didactic re-training sessions will be conducted annually and inter-rater reliability established at 6-month intervals to ensure that they meet at least 80% reliability of their measurement. Remediation and additional training will be provided as needed until competency was achieved.

D.5.6. PE Training, fidelity and supervision: Licensed doctoral-level psychologists and masters-level clinical social workers will deliver the PE treatment. Therapists will be existing VA clinicians who have been approved to donate time to the study and treat participants as part of their regular caseload. Supervision of PE will include regular review of session video to determine presence or absence of essential PE component, and monitor for protocol violations. Treatment sessions will be videotaped and 12% will be randomly selected and reviewed by PE expert ([name]) to ensure fidelity to the treatment manual (15 sessions will be selected from sessions 1–2, session 4, sessions 6–9, and sessions 10 and above).

D.6. Outcome Measures.

D.6.1. Primary Outcome Measure: The primary outcome is the difference in PTSD symptom severity from baseline to week 12 measured by the 30-item **CAPS-5** past month version (for current PTSD) total score(Weathers et al., 2018).

D.6.2. Interview based Assessments: We will collect demographic data using the **PhenX Measures** for Mental Health (<https://www.phenxtoolkit.org>). History of psychiatric risk factors will be obtained by initial interview. Comorbidity and potential exclusionary diagnosis will be determined by **M.I.N.I.** (Sheehan et al., 1998) We will exclude individuals with psychosis related disorders, bipolar I and II disorder, and alcohol/illicit substance use disorder within 6 months of initial assessment as the use of ketamine will be contraindicated. A widely used brief screening test, the **MMSE** will quantitatively assesses for exclusion of moderate-to-severe cognitive impairment cognitive. All study-related audio recordings will be maintained in accordance with the Record Control Schedule (i.e., 6 fiscal years after study closure).

D.6.3. Secondary Outcome Measures: Severity of depression would be measure by the **MADRS**, a semi-structured 10-item scale designed to be particularly sensitive to change over time in patients treated with antidepressant medication. The MADRS is psychometrically sensitive to assess the rapid onset of antidepressant efficacy (Johnson et al., 2016). The **PCL-5** is a 20-item self-report measure that assesses the 20 DSM-5 symptoms of PTSD. For the study, the PCL-5 will serve to screen potential candidates for PTSD and to monitor symptom changes during and after treatment. A PCL-5 cut-point score of 33 has been advised as a reasonable value until further psychometric work is available. The time frame for PCL-5 has been modified to meet research needs as in other studies (e.g., NCT02655692). Moreover, the Mental Illness Research, Education and Clinical Centers (mirecc.va.gov) stated that “The PCL can be easily modified to fit specific time frames or events. For example, instead of asking about ‘the past month,’ questions may ask about ‘the past week’ or be modified to focus on events...”. The **BAI** will serve as the gold standard self-report measure of general anxiety symptoms to distinguish anxiety from comorbid conditions such as depressive symptoms. The **C- SSRS- last visit version** will be used to count prospective or treatment emergent suicidal behaviors. The C- SSRS has been used in many treatment trials, and to measure treatment emergent suicidal events during pharmacotherapy(Mann et al., 2006). **SUDS**(Jaycox, Foa, & Morral, 1998) is a self-rating measure of distress ranging from 0 (complete relaxation) to 100 (maximum distress) and will measure activation of fear structure, decrease in fear during exposure sessions (within-session extinction); and decrease in initial reactions to the feared stimuli across sessions (between- session extinction). SUDS ratings correspond well with other indices of fear expression, including physiological indicators. Based on the PE protocol, the therapist will initially generate with the patient anchor examples at 0, 25, 50, 75, and 100 (e.g., 25: riding a roller coaster). SUDS will then be recorded every 5 min during the imaginal exposure. Peak SUDS scores, highest reported distress during first (Session 3) and last imaginal exposure session (Session 10-12), and mean SUDS scores, average reported distress during first (Session 3) and last imaginal exposure (Session 10-12), will be calculated. **NRS** (Ferreira-Valente, Pais-Ribeiro, & Jensen, 2011) is a one-dimensional measure of pain intensity in adults. The NRS is a segmented numeric version of the visual analog scale in which a whole number (0–10 integers) is selected to reflect the intensity of their pain anchored at 0 representing “no pain” and at 10 representing “worst pain imaginable”. The **CGI** (Busner & Targum, 2007)is a brief assessment consisting of a 3-item observer-rated scale that measures illness severity, global

improvement or change, and therapeutic response. The CGI has been widely used in clinical trials concerning psychotropic treatments. The **WHOQOL-BREF** ("The World Health Organization Quality of Life assessment (WHOQOL): position paper from the World Health Organization," 1995) is a 26-item brief assessment of quality of life in four factor-analytically confirmed dimensions: Physical, Psychological, Social, and Environmental. The **Credibility/Expectancy Questionnaire (CEQ)** (Devilly & Borkovec, 2000) is an 8-item scale of belief in the rationale and logic of a treatment (credibility) and belief in a likely positive outcome from a treatment (expectancy). The CEQ has been shown to predict treatment reactions in expected ways. The CEQ was modified slightly for this protocol to include questions about expectancy regarding changes in PTSD symptoms.

D.6.4. Side Effects Measures: We will monitor side effects during intervention and at follow-up visits. The **PRISE** (Rush et al., 2004) assess for the last 7 days the side effects in the following symptom domains; Gastrointestinal, Heart, Skin, Nervous System, Eyes/Ears, Genital/Urinary, Sleep, Sexual Functioning, and Other. Each domain has multiple symptoms which can be endorsed. The PRISE is used in combination with **FIBSER** (Wisniewski, Rush, Balasubramani, Trivedi, & Nierenberg, 2006) which rates the intensity, frequency and overall burden due to side effects in a 7-point Likert-type scale. During ketamine infusions, we will assess potential side effects by 1) the **CADSS** (Bremner et al., 1998), a clinician-administered tool validated in healthy subjects and patients with PTSD and designed to measure present-state perceptual, behavioral, and attentional alterations occurring during dissociative experiences; 2) the four-item positive symptom subscale of the **BPRS** (Zanello, Berthoud, Ventura, & Merlo, 2013) a clinician-rated tool that assess change in severity of psychopathology consisting of suspiciousness, hallucinations, unusual thought content, and conceptual disorganization; and 3) the **YMRS** (Young, Biggs, Ziegler, & Meyer, 1978), item #1 to evaluate possible manic symptoms. Finally, the **Modified Aldrete score system** (mAldrete)(Aldrete, 1995) is a set of criteria commonly used to assess transition from anesthesia to recovery. Numeric scores of 0, 1, or 2 are assigned to motor activity, respiration, circulation, consciousness, and SpO₂ level for a maximal score of 10. A score ≥ 9 is required for discharge from post-anesthesia care unit.

6.7. Data Analysis Plan.

6.7.1. Sample Details: *We propose a sample of 10 patients in this proof-of-concept pilot study.*

6.7.2. Data Collection: Study data will be collected and managed using VA REDCap (Research Electronic Data Capture) hosted behind the VA firewall on a VINCI server. REDCap is a secure, web-based application designed to support data capture for research studies, providing 1) an intuitive interface for validated data entry; 2) audit trails for tracking data manipulation and export procedures; 3) automated export procedures for seamless data downloads to common statistical packages; and 4) procedures for importing data from external sources.

6.7.3. Data Analysis: The data analyses will be performed by [name], Co-I on this project. Each subject will be assessed for the primary outcome variable (CAPS-5 score) at baseline (1-2 weeks prior to starting the intervention), week 4, and at the end of PE treatment (week 12). *Statistical analysis for this study will be essentially descriptive in nature. We will assess means, standard deviations, and 95% confidence intervals in symptoms at key assessment points. We will also examine distribution of missing data. In addition to the CAPS-5, we will also examine change in our secondary measures (PCL-5, CogState, MADRS, etc.), again these analyses will be descriptive in nature and will be used to refine our RCT proposal.*

6.7.4. Data Safety.

After the recruitment of 6 subjects, an independent, 3-person panel of physicians and researchers will conduct a reassessment of the risks and benefits to study participants. This panel will review all adverse events for severity and frequency.

6.8. Anticipated potential problems and alternative strategies.

The research infrastructure and SOPs to run ketamine infusions, and a well-established PTSD service are currently in place at MVA to assure timely start-up within 3 months. However, possible problems and solutions during execution of the study might be: 1) Slow recruitment/enrollment: We cautiously propose recruiting about 10 veterans aim to complete the primary outcome for our study. Nevertheless, if recruitment is slow, we would expand to include recruitment from satellites clinics within the Minneapolis VA Health Care System. In addition, we could reach out the Veteran's population served at the St. Cloud VA Health Care System (SCVAHCS) (see. 6.3.2. Feasibility of recruitment. 2) Dropouts and missing data: In our own sample, out of 16 subjects, only 2 dropped out in agreement with the literature that consistently supports tolerability of serial ketamine infusions. However, if risk of dropping out due to assessment burden occurs, subjects will have the option of completing a minimum core of primary outcome measures and maintain a flexible routine for recurrent appointments. For missing values, we will handle it by data imputation strategies, by last-

observation-carried-forward, and by the exclusion of dropouts (completers-only analyses); 3) Lost of follow-up: We would initiate outreach procedures and safety checks.

E. STUDY COMPENSATION

Participants will be compensated for completing the assessment sessions throughout the study. Assessment sessions involve individual clinical interviews, self-report, and semi-structured questionnaires. Compensation for assessment sessions will be delivered according to the following schedule: \$75 for Eligibility Screen and Baseline (1 week prior to starting treatment, approximately 3 hours), \$50 for each assessment during medication phase (total of 03 over 3 weeks; +/- 02 hrs. each), \$30 at post-ketamine PE sessions 4, 6, 8 and 12 (total of 04 over 2 months; +/- 02 hrs. each), and \$30 for monthly follow-up post-treatment (twice for +/- 02 hrs.) for a total of up to \$405. Participants who prematurely withdraw from study assessments will not be compensated for assessment sessions that have not yet taken place.

F. BIBLIOGRAPHY AND CITED REFERENCES

Abdallah, C. G., Adams, T. G., Kelmendi, B., Esterlis, I., Sanacora, G., & Krystal, J. H. (2016). KETAMINE'S MECHANISM OF ACTION: A PATH TO RAPID-ACTING ANTIDEPRESSANTS. *Depress Anxiety*, 33(8), 689-697. doi:10.1002/da.22501

Abbott, C. S., Lim, K. O., Forbes, M. K., Erbes, C., Tye, S. J., Grabowski, J. G., . . . Shiroma, P. R. (2018). Efficacy, Safety, and Durability of Repeated Ketamine Infusions for Comorbid Posttraumatic Stress Disorder and Treatment-Resistant Depression. *J Clin Psychiatry*, 79(3). doi:10.4088/JCP.17m11634

Abbott, C. S., Shiroma, P. R., Cullen, K. R., Johns, B., Thuras, P., Wels, J., & Lim, K. O. (2017). The Antidepressant Effect of Repeat Dose Intravenous Ketamine Is Delayed by Concurrent Benzodiazepine Use. *J Clin Psychiatry*, 78(3), e308-e309. doi:10.4088/JCP.16l11277

Aldrete, J. A. (1995). The post-anesthesia recovery score revisited. *J Clin Anesth*, 7(1), 89-91.

Averill, L. A., Purohit, P., Averill, C. L., Boesl, M. A., Krystal, J. H., & Abdallah, C. G. (2017). Glutamate dysregulation and glutamatergic therapeutics for PTSD: Evidence from human studies. *Neurosci Lett*, 649, 147-155. doi:10.1016/j.neulet.2016.11.064

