PE is considered a first-line evidence-based treatment for PTSD with compelling evidence to effectively reduce PTSD symptoms relative to waiting list(Powers, Halpern, Ferenschak, Gillihan, & Foa, 2010). A multi-center study(Schnurr et al., 2007) showed that female veterans and active-duty military personnel with PTSD were more likely than those in the present-centered therapy (PCT) group to no longer meet PTSD diagnostic criteria (41% vs 28%); however, PE achieved only an overall remission rate of 15% (vs 7% in PCT), the dropout rate was almost double in PE (38%) than in PCT (21%), and there was no significant difference in PTSD severity scores on the CAPS at 6-month follow-up with rates of PTSD remission at 40% in PE and 33% in PCT. A recent review of clinical trials of trauma-based therapies for PTSD (PE and Cognitive Processing Therapy [CPT]) in the military and veteran population found that between 30% to 50% of participants failed to attain clinically meaningful symptom improvement (defined as a 10- to 12-point decrease in interviewer- assessed or self-reported symptoms)(Steenkamp, Litz, Hoge, & Marmar, 2015). The mean posttreatment scores for CPT and PE remained at or above clinical criteria for PTSD, and approximately two-thirds of patients retained their PTSD diagnosis after treatment (range, 60%-72%)(Steenkamp et al., 2015). These results suggest that despite its efficacy, PE (and CPT) in the military/veteran population is suboptimal to relieve PTSD as an elevated number of patients drops out from treatment and most patients remain with considerable post-treatment residual symptoms.

A.3. Medication-enhanced psychotherapy.

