implementation on sub-anesthetic doses of intravenous ketamine as augmenting strategy of standardized, manually-driven PE in PTSD (*Figure 7*). For this purpose, we aim to: **1) clarify research hypotheses on the efficacy, safety and tolerability of this MEP approach; 2) assess the acceptability of methods and instruments to participants; 3) identify potential barriers to subsequent study completion, and 4) obtain estimates of means, standard deviation and 95% confidence intervals on outcome measures as well as the expected rates of missing data and participant attrition.** We estimate that analysis of data obtained from participation of 10 patients will provide responses to our scientific aims. Participants will be male and female veterans (18 to 75 years old) of any era or military background diagnosed with PTSD. Potential participants will be recruited from Mental Health clinics and screened for eligibility using a two-stage process (phone/chart review, followed by interview). Those who meet eligibility criteria will complete baseline assessment one week prior to starting treatment. Then, treatment will consist of 1) 3-week ketamine-PE phase composed by weekly single intravenous ketamine (0.5 mg/kg for 40 minutes) followed within 24 hrs. by PE session; and 2) ketamine-free PE phase from week 4 through 12. After PE is completed (session 12), patients will be assessed during a 2-month follow-up period at various time points. We estimate that 10 veterans will reach time point for primary outcome measure (CAPS score at week 12) and will be considered for primary analysis. Independent evaluation of PTSD, cognitive function, depression, anxiety and other potential covariates (i.e., pain) will be ascertained at baseline, at several time points during treatment, and at follow-up.

D.1.1. Design Considerations: As with any pilot study, several factors have been considered in the design of this proposal. The goal is to provide a design that is feasible, efficient, and above all, able to answer study aims. Some of the possible alternative designs, and reasons we did not select them, are listed.

Table 2. Considerations and Rationale for Choosing the Current Design

Consideration	Rationale

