Our planned enrollment includes 10 patients to receive three weekly ketamine-PE treatment followed by ketamine-free PE treatment for 9 additional weeks. Participants will be recruited from veterans receiving mental health treatment. Referrals will occur from VA clinicians and clinics, and responses from posted fliers and study pamphlets. Potential participants will be provided with information about the study and screened through medical records, chart review, and by telephone to determine whether they meet basic inclusion/exclusion criteria. Those who qualify will be scheduled for a more rigorous assessment (*see further details below*).

D.3.1. Eligibility Criteria: The following eligibility criteria will be used to identify a broad array of participants with PTSD considered suitable for the study.

Table 3: Eligibility Criteria

Inclusion Criteria	Exclusion Criteria

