
 1. Male or female Veterans aged 18-75 years old. 2. Diagnosis of chronic (minimum of three months) PTSD (Clinician-Administered PTSD Scale for DSM-5 -CAPS-5 score >33). 3. Voluntarily eligible to participate in PE. 4. Severity of PTSD symptoms defined by PCL-5 >33. 5. Psychotropic medications on stable doses (no dosing adjustments/changes for ≥ 4 weeks; ≥ 6 weeks for fluoxetine) prior to beginning of the study. 	
 1. Unwillingness/unable to sign informed consent. 2. Previous or current participation in trauma-exposed therapy and/or ketamine treatment. 3. Evidence of mental retardation, pervasive developmental disorder and/or moderate/severe cognitive impairment (MMSE scores ≤ 27). 4. Any unstable medical or non-psychiatric CNS condition. 5. Lifetime history of psychosis-related disorder, bipolar disorder I or II disorder, or any condition other than PTSD judged to be the primary presenting psychiatric diagnosis. 6. Moderate to severe traumatic brain injury (mental status change or loss of consciousness > 30 min; Glasgow Coma Scale < 13; post-traumatic amnesia > 24 hours; visible lesion on CT/MRI brain scan). 7. Active alcohol/illicit substance use disorder within 6 months of initial assessment; presence of illicit drugs by positive urine toxicology. 8. For women: pregnancy (confirmed by lab test), initiation of female hormonal treatments within 3 months of screening, or inability/unwillingness to use a medically accepted contraceptive method during the study. 9. Imminent risk of suicidal/homicidal ideation and/or behavior with intent and/or plan

D.3.2. Feasibility of recruitment: The study will recruit 10 Veterans over 12 months. In the last 12 months, 289 Veterans were diagnosed with PTSD and 114 have received at least 02 PE sessions at the MVA. While we do not anticipate any difficulties, we could expand recruitment to satellite clinics from MVA Health Care System.

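### D.1 expects 10 veterans to reach the week-12 CAPS-5 from a planned enrolment of 10, which holds only if nobody is lost

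*Combined protocol and SAP*

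**What the plan says.** Section D.1 gives the evaluable number: "We estimate that 10 veterans will reach time point for primary outcome measure (CAPS score at week 12"), and the same sentence says these veterans will be considered for the primary analysis.

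The number entering the study is given in three other places:

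- D.3: "Our planned enrollment includes 10 patients to receive three weekly ketamine-PE treatment"
- D.3.2: "The study will recruit 10 Veterans over 12 months"
- 6.7.1: "We propose a sample of 10 patients in this proof-of-concept pilot study"

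Section 6.8 is looser: "We cautiously propose recruiting about 10 veterans aim to complete the primary outcome for our study". The remedies listed there (satellite clinics, a second VA system) address slow recruitment. No section states over-enrolment, replacement of dropouts or a planning rate for attrition.

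The plan nevertheless foresees loss. Aim 4 in D.1 includes estimating "the expected rates of missing data and participant attrition". Section 6.8 lists imputation, last observation carried forward (LOCF) and a completers-only analysis for missing values. It also reports the team's own experience: "In our own sample, out of 16 subjects, only 2 dropped out in agreement with the literature". Section A.2 cites a multi-center trial in which 38% dropped out of PE, against 21% in the comparison therapy.

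**The concern.** If 10 are enrolled and 10 are expected to reach week 12, the implied loss over 12 weeks of treatment is zero. That does not fit a plan that sets out to measure attrition, prepares three ways of handling missing values, and presents dropout from PE as a known weakness of the therapy in this population.

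At stake is the size of the primary analysis as described to a reader of D.1. The pilot exists partly to supply means, standard deviations, confidence intervals and attrition rates for a later trial. A reader should be able to see how many week-12 measurements it can realistically deliver.

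**Working it through.** **Inputs**

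| Input | Value | Source |
|---|---|---|
| Planned enrolment, N | 10 | D.3, D.3.2, 6.7.1 |
| Veterans expected at week 12 | 10 | D.1 |
| Dropout, team's earlier ketamine series | 2/16 = 12.5% | 6.8 |
| Dropout, PE in the cited trial | 38% | A.2 |

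The plan gives no power or precision formula for N = 10, so the relation to check is: expected number at week 12 = N × (1 − d), where d is the proportion lost.

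**Reproducing the plan's figure.** With d = 0, 10 × (1 − 0) = 10. The D.1 figure is reproduced exactly, and only at d = 0.

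**Applying the document's own dropout figures.** Assume that a dropout has no week-12 CAPS-5 and that losses are independent between patients. The chance that all 10 are observed is (1 − d)^10.

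| Scenario | Expected of 10 | Chance of 10 of 10 |
|---|---|---|
| d = 12.5% | 10 × 0.875 = 8.75 | 0.875^10 = 0.263 |
| d = 38% | 10 × 0.62 = 6.2 | 0.62^10 = 0.0084 |
| d = 19% (assumption: half of those who stop PE are still assessed) | 10 × 0.81 = 8.1 | 0.81^10 = 0.122 |

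The counts in the second column are expectations, not bounds. For even odds that all 10 are observed, solve (1 − d)^10 = 0.5, giving d = 1 − 0.5^(1/10) = 0.067. Loss would have to be 6.7% or less per patient.

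**How firm the two rates are.** The 2 of 16 comes from six infusions in 12 days without PE (3.3.1, under B.2). Its exact (Clopper-Pearson) 95% interval is 1.6% to 38.3%. The 38% is dropout from PE without ketamine, in female veterans and active-duty personnel (A.2). Neither is a forecast for three weekly infusions combined with 12 weeks of PE.

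**Effect on precision.** The half-width of a 95% t-interval for a mean, in SD units, is t(0.975, n − 1)/√n:

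- n = 10: 2.262/3.162 = 0.72
- n = 9: 2.306/3.000 = 0.77 (7% wider than at n = 10)
- n = 6: 2.571/2.449 = 1.05 (47% wider)

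**The case against.** The strongest reply is that D.1 offers an estimate, in a pilot meant to learn the attrition rate, and that 6.8 qualifies the number with *about* and frames completion as an aim. That is fair as to tone. It does not change D.3, D.3.2 and 6.7.1, which put enrolment or sample at 10. If 10 completers were the target, more than 10 would have to be enrolled, and no section says so.

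A second reply is that imputation or LOCF can keep all 10 in an analysis, since a week-4 CAPS-5 is scheduled (D.5.2) and could be carried forward. This stands as far as inclusion in an analysis goes. But the D.1 sentence says the veterans will reach week 12, which a patient with an imputed value has not done, and a completers-only analysis is also listed.

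A third reply is that retention may be better here. A.6.2 suggests that targeting depression or anxiety may improve it, and 6.8 offers a reduced core assessment. Both are possible, which is why the rates above serve only as scenarios.

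A reader might also infer three stronger things that the documents do not support:

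- *That the pilot's confidence intervals will be too narrow.* They will be computed from the patients observed; nothing in D.1 or 6.7.3 derives precision from the planned 10.
- *That the 2 of 16 in 6.8 contradicts the statement in 3.3.1 that sixteen veterans completed six infusions.* The two fit together if the losses came during follow-up. The F statistic in 3.3.1 has 6 and 90 degrees of freedom. In an ordinary repeated-measures analysis with seven time points, 6 × (16 − 1) = 90, which fits 16 patients through the sixth infusion. Some remission figures do imply a denominator of 15: 12 remitters at 80.0%, and six people as 40% of the sample. That is a separate reporting point about background data and does not affect this trial's evaluable number.
- *That enrolment must rise.* The plan makes no power claim and promises no interval width, so nothing in it requires 10 completers.

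**Conclusion.** The point holds and is minor. D.1 states an evaluable number that the planned enrolment delivers only with zero loss, while the plan expects loss. On the document's own dropout figures, about 9 (12.5% lost) or about 6 (38% lost) of 10 would have an observed week-12 CAPS-5, and the chance of all 10 is 26% or 0.8%. These results assume independent losses and no week-12 assessment after dropout, and both rates come from other regimens. The conclusion that 10 of 10 requires zero loss needs neither rate.

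The harm is limited to a stated evaluable number that is too favourable. The analysis in 6.7.3 is descriptive, its intervals will reflect the observed n, and no test, threshold or conclusion depends on reaching 10.

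**What to change.** Keep enrolment at 10 and replace the D.1 sentence with wording such as: *10 veterans will be enrolled; fewer than 10 are expected to provide an observed week-12 CAPS-5 (about 9 if 12.5% are lost, about 6 if 38% are lost, as scenarios).*

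Two additions are optional:

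- In 6.7.1, note that the 95% confidence interval half-width for a mean is 0.72 SD at n = 10, 0.77 SD at n = 9 and 1.05 SD at n = 6.
- In 6.7.3, report week-12 CAPS-5 retention with an exact 95% confidence interval. Aim 4 already seeks the rate; only the interval is new.

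The cost is one sentence in D.1 and, if the options are taken, one each in 6.7.1 and 6.7.3. No patients or visits are added and the planned missing-data analyses are unchanged. The denominators of the earlier series can be clarified separately; the change does not wait on them. The downside is that the stated evaluable number becomes less favourable.
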